Finally, micronutrient deficiencies and excess may cause genomic damage, which could be in the same range of magnitude, or even higher, than genomic damage caused by exposure to high doses of environmental genotoxic agents such as carcinogenic agents, ultraviolet radiation and ionizing radiation (Fenech, 2010). Furthermore, since iron is not easily eliminated from the body and participates in the cell redox reactions, where ROS generate through Fenton reactions, increased iron concentrations could damage proteins, lipids and DNA permanently, causing structural and functional impairments. High plasma iron concentrations may amplify the effect of free radicals (Aksu, 2010); although cells have developed different mechanisms to reduce iron toxicity, including the regulation of iron transport through cell membranes and the production of ROS-eliminating enzymes. An imbalance of these systems caused by excess iron could increase oxidative damage susceptibility that could cause an increase in the mutation rate. These could increase the risk of developing neoplastic processes, diabetes and cardiovascular and neurological disease (Evans, 2004; Liu, 2009; Toxqui, 2010).

The effect of treatment with iron on DNA oxidation has been investigated in children with IDA, observing a significant increase of DNA strand breaks and baseline oxidative DNA damage as compared with children not receiving treatment (Aksu, 2010). However, we have not found evidence in the literature about the effect of preventive doses of iron supplementation on DNA. Therefore, we propose to compare the effectiveness of weekly and daily supplementation for the prevention of anemia in infants less than six months of life and to analyze their impact on genomic stability.

Objectives

General: To compare the effectiveness of weekly and daily iron supplementation for the prevention of anemia in infants.

Specific: To compare:

- To compare the effectiveness of weekly, daily and no iron supplementation at six months of age in EBF infants.
- To compare the effectiveness of weekly and daily iron supplementation in six-month-old infants receiving MF.
- To compare the incidence of adverse effects for weekly and daily iron supplementation at six months of age.
- To compare the adherence to treatment of weekly and daily iron supplementation at six months of age.
- To compare the concentration of oxidative stress biomarkers for both types of iron supplementation.

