- To compare the genomic damage in both types of iron supplementation.

Study hypothesis

Weekly ferrous sulfate supplementation will be more effective in the prevention of IDA in infants than daily supplementation due to a higher adherence and a lower incidence of adverse effects. Weekly iron supplementation will cause less genomic instability as compared with daily iron supplementation.

Study design

Randomized controlled clinical trial.

Study sample

Eligibility

Infants performing monthly health controls at the Pediatric Health Observatory of IDIP, La Plata Children's Hospital, from birth to six months of age will be included in the study.

Inclusion, exclusion and elimination criteria

Inclusion criteria: Three-month-old clinically healthy breastfeeding infants with birth age > 37 weeks, birth weight between 2500 and 4000 g, a normal fetal and neonatal history, that attend IDIP's Health Observatory and whose parents/guardians express the will to participate in the study and sign a written informed consent form.

Exclusion criteria: Anemic and/or iron deficient infants or with chronic diseases or acute infections or under antibiotic/vitamin treatment within 15 days prior to the study.

Elimination criteria: infants with severe intolerance to iron preventive supplementation, who will receive the alternative preventive treatment with ferrous fumarate or iron polymaltose complex).

Unit of analysis: Three to six month-old infants.

Sample size and selection

According to ENNyS, the prevalence of anemia in 6-9 months old infants is 50.8%. Our controlled interventions would reduce such prevalence to 30%. Sample size was estimated with 0.95 significance level and 0.80 power, resulting in 174 infants (n= 87 for each supplementation group). This number was adjusted considering a 15% dropout, thus enrolling 204 infants.

Methods

Operational definition of variables

Main variables

-Anemia is defined as the “decrease in the total amount of blood cells or a blood hemoglobin (Hb) concentration more than 2 standard deviations below the mean of an age- and sex-matched reference range”. We will define the presence of anemia when Hb < 9.5 g/dL at 3 months of age and Hb < 11.0 g/dL at six months of age (CDC, 2007).

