- Genomic damage: DNA damage assessed by cytomolecular techniques using the Comet assay (damage index assessment in 200 cells, quantifying damage by Tail moment and Olive Tail moment). The frequency of oxidized DNA bases will be determined by competitive 8-oxo-dG Elisa.

Other variables:

- Sex, weeks of gestation, umbilical cord clamping.

- Infant nutritional condition will be assessed by anthropometry (weight, height, head circumference) at three and six months.

- Sociodemographic data of infants and relatives, including place of residence, unsatisfied basic needs, maternal education.

- Maternal nutritional condition will be evaluated with anthropometry and iron status.

- Environmental exposure to genotoxic agents (antibiotics, radiation (X-rays) and chemical substances like pesticides, solvents and industrial waste) will be assessed by questionnaire.

Data collection

-Patient enrolment

During health control visits to IDIP Health Observatory on the first and second month of life, parents and tutors will be invited to participate in the study; the study's protocol, its aims and benefits will be explained in a plain language. They will be asked to sign a written informed consent form in case they accept their children be incorporated to the study. Infants meeting the inclusion criteria with exclusively breastfeeding (EBF) will be randomly divided into three groups: weekly, daily and no supplementation. Those with mixed feeding (breastfeeding and formula; MF) will be randomly divided into two groups: weekly and daily supplementation.

- Intervention

Weekly supplementation (EBF or MF): infants will receive a weekly dose of ferrous sulfate (4mg/kg/week).

Daily supplementation (EBF or MF): infants will receive a daily dose of ferrous sulfate (1 mg/kg/day).

Without intervention (only EBF): infants will receive no supplementation, following the current SAP guidelines. Ferrous sulfate will be supplied by pediatricians.

- Randomization

Randomization will be performed by computer-generated random sequences of numbers in blocks of variable length. Randomization will be stratified by type of intake (EBF or MF).

Treatment assignments will be placed in sequentially numbered, opaque and sealed envelopes which will be consecutively put in a box and later removed one at a time. The person in charge of the random allocation process will not take part in the enrollment process.

- Blinding

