Blood samples (3 ml) from infants will be drawn at IDIP’s laboratory by venipuncture and divided into two vials: 1) an EDTA tube containing 1 ml blood for complete blood count, and 2) lyophilized lithium heparin tube that will be centrifuged to obtain plasma for the assessment of ferritin, CPR, sTfR, 8-oxodG and TBARS, and erythrocytes for the assessment of CAT and SOD determinations and for the Comet assay. The following methods will be used:

Hemoglobin: Modified Drabkin method (ABX Pentra DX 120 Horiba).

Ferritin and sTfR: enzymatic immunoassay using a chemiluminescence substrate (Access-Beckman Coulter, Fullerton, US).

C-reactive protein: turbidimetry (Autoanalyzer BT 3000 Plus Wiener).

All these tests will be performed at the Children’s Hospital Central Laboratory.

Cytomolecular genomic stability: alkaline version of the Comet assay (electrophoresis of a cell sample previously embedded in agarose, being migration proportional to the damage present (Sinh et al., 1988, Padula 2016).

ROS-mediated DNA damage: ELISA to quantify 8-oxodG, the most frequently oxidized nucleotide (Rossner et al 2006; Rossner & Sram 2012).

These tests will be performed at IGEVET.

CAT activity: spectrophotometry using Aebi’s method.

SOD activity: commercial kit (Ransod; RandoxLabs).

TBARS: spectrophotometry according to Okhawa.

These tests will be performed at IDIP and IGEVET.

Iron nutritional status (hemoglobin and ferritin) of mothers: blood samples taken at three and six months after delivery.

Data analysis

The effectiveness of the interventions will be evaluated at six months of age by comparing the incidence of anemia in both study groups as a relative risk (RR) and its corresponding 95% confidence interval (95% CI). For the EBF group, no supplementation will be the reference category, whilst for the MF group, the reference category will be daily iron supplementation.

Intention-to-treat analysis will be used to account for the possible changes in type of feeding and/or intervention arms. However, per-protocol analysis will be also performed and compared with intention-to-treat analysis in order to determine the result robustness.

Losses to follow-up will be censored since analyses will be performed in closed cohorts because we will not be able to estimate incidence density (we will only collect data on anemia and ID at three and six months).

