We will also determine the incidence of adverse effects and the incidence of low treatment adherence at six months of age for weekly vs. daily iron supplementation in both EBF and MF and calculate RR (95% CI) at six months of age.

[figure not shown]
Means and differences of enzymatic SOD and CAT activity and TBARS concentration at three and six months will be compared in both study groups. The same will apply to the Comet and 8 oxodG assays. Differences between groups will be determined by Anova or Kruskal-Wallis test for quantitative variables with post-hoc comparisons and Chi-square for categorical variables. Within group comparisons will be analyzed using Student's or Wilcoxon test.

Risk of bias assessment

Selection bias could be present since parents/tutors willing to participate could show higher interest in the research project than those who do not participate. Considering that the population sample attends for monthly controls, a trust relationship may be established between parent/tutor and pediatrician, resulting in a higher degree of adherence to supplementation than in the general population.

Project Schedule

Study flowchart

Work plan

SPECIFIC OBJECTIVE 1: Compare the effectiveness of weekly, daily and no iron supplementation in EBF infants.

SPECIFIC OBJECTIVE 2: Compare the effectiveness of weekly, daily and no iron supplementation in MF infants.

| ACTIVITY | RESPONSIBLE | EXPECTED RESULT |
|--|----------------------------|--|
| Enrollment of infants according to the inclusion criteria. | Pediatricians | Incorporate infants who comply with inclusion criteria |
| Informed consent. | | |
| Intervention assignment. | Statistician | Random allocation |
| Blood sample collection. | Laboratory technician | Adequate specimen collection (enough volume, non clotted) |
| Hemoglobin, ferritin, PCR and sTfR determinations. | Biochemists | Assessment of the prevalence of anemia and iron deficiency |
| Indication for and monitoring of the intervention | Pediatricians | Complete registry of the intervention. |
| Text message reminders | Pediatricians | Intervention adherence. |
| Weight and height measurement. | Pediatrician, Nutritionist | Determine the anthropometric nutritional condition. |
| Registry of data. | Data entry | Complete database. |
| Data analysis and interpretation of results. | Team, Statistician | Report of results and conclusions. |

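### The anemia relative-risk references yield the main contrast, weekly versus daily iron, only in mixed-fed infants, and no estimate over both feeding strata is described

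*Protocol*

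**What the plan says.** **Objectives, general:** "To compare the effectiveness of weekly and daily iron supplementation for the prevention of anemia in infants". The aim is not limited to a feeding type.

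**Study hypothesis:** "Weekly ferrous sulfate supplementation will be more effective in the prevention of IDA in infants than daily supplementation". Again there is no restriction by feeding.

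**Objectives, specific (EBF):** "To compare the effectiveness of weekly, daily and no iron supplementation at six months of age in EBF infants". This three-way comparison includes the weekly/daily pair. A separate specific objective covers weekly versus daily in MF.

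**Patient enrolment and Randomization:** EBF infants "will be randomly divided into three groups: weekly, daily and no supplementation"; MF infants are randomized to weekly or daily. Randomization is stratified by feeding type.

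**Data analysis, anemia:** effectiveness at six months is assessed by "comparing the incidence of anemia in both study groups as a relative risk (RR) and its corresponding 95% confidence interval (95% CI"). The next sentence sets the references: "For the EBF group, no supplementation will be the reference category, whilst for the MF group, the reference category will be daily iron supplementation".

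**Data analysis, other outcomes:** for adverse effects and low adherence, the protocol explicitly names RRs for weekly against daily in EBF as well as in MF. For the oxidative stress biomarkers it again uses the two-group phrase: "TBARS concentration at three and six months will be compared in both study groups".

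**The concern.** The stated references produce three anemia RRs: weekly versus none in EBF, daily versus none in EBF, and weekly versus daily in MF. The comparison that defines the trial is therefore specified in one of the two strata in which it is randomized. Nothing is said about an estimate over both.

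The sentence before the reference rule does not settle this. Its two study groups could be weekly and daily, as the biomarker sentence suggests, or EBF and MF. On the first reading an overall weekly-versus-daily RR may be intended, but its reference and the handling of the strata are not given.

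Two things are at stake. Read by its reference rule, the plan answers the general objective with fewer infants, and so a wider interval, than the randomized data allow. Read the other way, the choice between an MF-only, an EBF and a combined RR for the main outcome stays open and could be made after results are known.

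**Working it through.** **1. Contrasts asked for and contrasts named**

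| Weekly vs daily | Randomized? | In the objectives? | Anemia RR given by the references? | RR named for adverse effects and adherence? |
|---|---|---|---|---|
| in EBF | yes | yes (specific, EBF) | no | yes |
| in MF | yes | yes (specific, MF) | yes | yes |
| over both | yes, stratified | yes (general) | not described | not described |

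**2. The protocol's sample size.** Inputs from Sample size and selection: 50.8% versus 30%, power 0.80. The stated 0.95 significance level is read as two-sided alpha 0.05. With pooled variance under the null and mean risk 0.404:

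n = [1.96·√(2·0.404·0.596) + 0.842·√(0.508·0.492 + 0.30·0.70)]² / 0.208² = 86.2, so 87 per group.

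This reproduces the stated figure, "resulting in 174 infants (n= 87 for each supplementation group"). It is a two-group calculation.

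**3. Share of the weekly/daily infants outside the MF-only RR.** The EBF share s and the allocation ratio are not stated. I assume s = 30%, 50% or 70% and equal allocation within strata. The share of iron-allocated infants who are EBF is

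L = (s/3) / [s/3 + (1−s)/2] = 0.222, 0.400, 0.609.

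**4. Loss of precision.** If risks are equal in the two strata, the ratio of SE(log RR), MF alone to both strata, is

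1/√(1−L) = 1.13, 1.29, 1.60.

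This ratio does not depend on the total sample size.

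**5. Intervals around RR = 1.** Assume 87 infants in each iron arm (the literal wording, with the no-supplementation arm extra) and 30% risk in both arms. SE(log RR) = √[2·(0.7/0.3)/n], and the 95% CI is exp(±1.96·SE).

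| EBF share | n per arm, MF | MF only | n per arm, EBF | EBF only | Both strata (87 per arm) |
|---|---|---|---|---|---|
| 30% | 67.7 | 0.60–1.67 | 19.3 | 0.38–2.62 | 0.64–1.57 |
| 50% | 52.2 | 0.56–1.80 | 34.8 | 0.49–2.05 | 0.64–1.57 |
| 70% | 34.0 | 0.48–2.07 | 53.0 | 0.56–1.79 | 0.64–1.57 |

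**6. Power, for illustration only.** The protocol does not state 50.8% versus 30% as a weekly-versus-daily effect. Power = Φ{[0.208 − 1.96·√(2·0.404·0.596/n)] / √[(0.508·0.492 + 0.30·0.70)/n]}.

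| EBF share | 87 per iron arm: MF only / both | 174 includes the no-supplementation arm: MF only / both |
|---|---|---|
| 30% | 70% / 80% | 65% / 76% |
| 50% | 58% / 80% | 51% / 73% |
| 70% | 41% / 80% | 33% / 69% |

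In the last column, n per arm is 60.9, 43.5, 26.1 in MF and 78.3, 72.5, 66.7 over both strata. A simulated stratified Mantel-Haenszel test (200,000 runs, no continuity correction, whole-number arms, same risks in both strata) gave 81% at all three EBF shares for 87 per iron arm, and 76%, 74% and 69% for the other reading. The closed-form figures for both strata are therefore close.

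**7. Can the EBF contrast be read off the planned output?** The point estimate can: it is the ratio of the two RRs against no supplementation. Its interval cannot be obtained from their two intervals, because both RRs share the reference arm. With an illustrative 30 per arm, risks of 30% in the iron arms and 50.8% in the reference arm, the direct SE of the log RR is √[2·0.7/(30·0.3)] = 0.394. Treating the two RRs as independent adds 2·0.492/(30·0.508) to the variance and gives 0.469.

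**The case against.** The strongest defence is that the rule is coherent. The protocol describes current national guidance as daily iron for young MF infants and iron only from six months for EBF infants, and says that the untreated EBF arm follows that guidance. The references therefore match current practice in each stratum. The protocol does not give this reason, but it is plausible. It explains the rule without making the rule deliver the general objective.

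A reference category also does not forbid other contrasts, and the EBF weekly/daily RR can be computed from the same counts. That stands: no data are lost. But the interval does not follow from the planned RRs, and the general chi-square line for categorical variables gives neither an RR nor a combined estimate.

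Reporting by stratum is legitimate, and how strata are combined is often left to a statistical analysis plan. This too stands in part: a missing estimator would not be a finding. The point is the reference rule that the protocol itself states. If reporting by stratum is intended, weekly versus daily is still missing in EBF.

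The two study groups may well mean weekly and daily; the biomarker sentence and the two-group sample size both favour that. Then the contrast is planned, but its reference and strata remain unfixed next to a rule set by feeding type.

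Finally, the sizes rest on assumed inputs. That is correct, and they are illustrations. The direction holds for any EBF share above zero.

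**Conclusion.** The concern holds and should be fixed; confidence is moderate, because the sentence before the reference rule can be read in two ways. As stated, the references give the trial's main contrast with a confidence interval in MF infants only, while the protocol names the same contrast in both strata for adverse effects and adherence.

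Under the assumed EBF shares, between about a fifth and three fifths of the iron-allocated infants are left out of that RR, and its log-scale interval is about 13% to 60% wider than over both strata. This assumes equal allocation within strata and equal risks in the two strata. The power figures are secondary, since the rates used are not a weekly-versus-daily effect.

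No flaw in design, endpoint or data collection follows from this point.

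**What to change.** In Data analysis:

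- State the weekly-versus-daily anemia RR (95% CI) at six months over both strata, stratified by feeding type at randomization (for example Mantel-Haenszel), as the analysis of the general objective.
- Report the weekly-versus-daily RR also within EBF and within MF.
- Keep weekly versus none and daily versus none in EBF as further contrasts.
- Say what the two study groups are.
- An interaction test is optional.

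If the team does not want to combine strata, it should say so and name the weekly-versus-daily RR within EBF.

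The cost is two or three sentences, with no change to randomization, endpoint or data collection. The downside is that a combined RR assumes a broadly common effect across feeding types. The stratum-specific RRs allow only a rough check of this, because the EBF estimate alone is imprecise, as the intervals above show.

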Study Protocol

OFFICIAL TITLE

Effectiveness of weekly and daily iron supplementation for the prevention of iron-deficiency anemia in infants. Impact on genomic stability.

NCT ID not yet assigned

03/01/2017

BRIEF TITLE

Iron deficiency anemia, iron supplementation and genomic stability in infants.

BRIEF SUMMARY AND DETAILED DESCRIPTION

Iron deficiency is the most prevalent nutritional deficiency and the main cause of anemia. Globally, 43% of pre-school children have anemia. In Argentina, the National Nutrition and Health Survey reported that 34.5% of children less than two years of age and 50.8% of 6 to 9-month-old infants were anemic. Although daily iron supplementation is supported as a preventive strategy, adherence is low in our country due to adverse effects and low prescription rates. Likewise, excess iron may cause genomic instability and thereby structural and functional alterations in proteins, lipids and DNA. Such damage may be permanent and lead to the development of neoplastic processes, diabetes and cardiovascular disease. Weekly iron supplementation is proposed as an effective alternative for older children and pregnant women, but evidence of such an effect in infants is scarce. The aim of this study is to compare the effectiveness of weekly and daily (current prescription) iron supplementation to prevent anemia in infants and to analyze its impact on genomic stability. We will perform a randomized, controlled clinical trial in infants that attend IDIP's Health Observatory for periodic health controls. Infants with exclusively breastfeeding (EBF) will be randomized into three groups: daily and weekly iron supplementation and no supplementation. Infants receiving both breastfeeding and infant formula i.e. mixed feeding (MF) will be randomized into two groups: daily and weekly iron supplementation. We will study anemia, iron status and genomic stability before supplementation (at 3 months) and at 6 months. Weekly iron supplementation is expected to be more effective than daily supplementation for the prevention of infant iron-deficiency anemia due to a higher adherence and a lower incidence of adverse effects. Further, genomic stability is also expected to be lower. We expect that our results will allow to revise the current supplementation schedules (start, frequency, dose, EBF) on scientific grounds and improve the economic resources devoted to anemia prevention (lowering medication expenses).

TECHNICAL DESCRIPTION

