At early life stages, IDA impacts strongly on public health. Therefore, research on alternative preventive solutions has been encouraged. The WHO endorses the general agreement that infant and pregnant women iron supplementation is a priority strategy when IDA prevalence in a particular group of individuals is higher than 40% (WHO, 2001). In Argentina, the Argentine Pediatrics Society recommends daily ferrous sulfate supplementation in infants less than 4 months of age receiving MF and from 6 months onwards in infants with EBF (SAP 2009). Despite ferrous sulfate is prescribed and freely supplied through the health program *Remediar*, adherence is low due to gastrointestinal adverse effects, mothers' neglect and low rate of prescription by healthcare team members (Christensen 2013, Bernstein 2008).

On the other hand, it has been pointed out that daily oral iron supplementation reduces iron absorption a few days after treatment initiation, whereas intermittent doses maximize absorption because iron

provision is concomitant with intestinal cell turnover (Anderson 2005; Frazer 2003a; Frazer 2003b). It is postulated that daily iron doses saturate the transport mechanisms, and that this correlates with intolerance symptoms, whilst weekly doses optimize absorption through transport mechanisms, decreasing intolerance symptoms (Viteri 1997, Srigiridhar 2001). On this basis, weekly iron supplementation is proposed as an effective IDA preventive alternative for older children and pregnant women (WHO 2011, De Regil 2011, Peña- Rosas 2012). Although different studies report the use of weekly iron supplementation, age-groups are dissimilar and include anemic patients; therefore, treatment instead of prophylactic doses are used (Coutinho 2008, Lima 2006). Meanwhile, evidence of weekly preventive supplementation in infants less than 6 months is scarce (Yurdakov 2004).

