-Iron deficiency is defined as insufficient iron in the body. It will be considered when blood ferritin <12 ng/ml (WHO 2001). Since ferritin is an acute phase reactant, we will measure C-reactive protein (CRP) to assess an eventual inflammatory state. When CRP is ≥ 5 mg/L, ID will be defined by a blood ferritin <30 ng/ml. The soluble transferrin receptor (sTfR) which is not influenced by inflammation will also be used (cut-off value, sTfR 8.3 mg/L) (Grant 2012).

Secondary variables

-Adverse effects: presence (or absence) and frequency of one or more of the following effects during ferrous sulfate supplementation (rejection, constipation, vomiting, diarrhea, abdominal pain).

-Adherence to treatment: is the rate of adherence to medication intake, dietary plan or lifestyle changes according to recommendations agreed on with healthcare professionals (OMS, 2003).

Adherence will be measured with the formula:

$$\frac{(\text{ml SO}_4\text{Fe received} - \text{ml SO}_4\text{Fe remaining})}{\text{days between the medication vial delivery and its return}} \times 100$$

where ml SO₄Fe received is the volume of ferrous sulfate delivered in a vial, sufficient to cover the prescription until the infants' next control (1 month), and ml SO₄Fe remaining is the residual volume in the vial at the moment of the health control.

We will consider low adherence the consumption of less than 50% of the amount of medication

prescribed for the study period, and less than 50% of intakes prescribed for the study period.

We will consider high adherence consumption of more than 80% of the amount prescribed and more than 80% of the intakes prescribed.

All combinations not covered by low and high adherence will be considered as moderate adherence.

-Genomic instability: Chromosome, DNA and cell damage caused by certain agents. We will evaluate oxidative stress and genomic damage at cytomolecular level and at DNA base level.

- Oxidative stress: imbalance between reactive oxygen species (ROS) production and accumulation and the counteracting enzymatic/non-enzymatic antioxidant mechanisms. We will measure catalase and superoxide-dismutase enzymatic activity and evaluate cell damage by lipid peroxidation through thiobarbituric acid-reactive substances (TBARS) assessment.

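### Agreement between per-protocol and ITT is the stated robustness check, yet the hypothesised advantage of weekly iron runs through adherence, so the two analyses are expected to differ if the hypothesis is true

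*Protocol*

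**What the plan says.** All references are to the protocol.

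- **Data analysis** names ITT first and gives its purpose: "Intention-to-treat analysis will be used to account for the possible changes in type of feeding and/or intervention arms". It then adds that "per-protocol analysis will be also performed and compared with intention-to-treat analysis in order to determine the result robustness". It does not say which infants form the per-protocol set, or what follows if the two analyses differ. Losses to follow-up are censored.
- **Study hypothesis**: "Weekly ferrous sulfate supplementation will be more effective in the prevention of IDA in infants than daily supplementation due to a higher adherence", with fewer adverse effects as the second reason. The **Brief summary** gives the same pathway: "prevention of infant iron-deficiency anemia due to a higher adherence and a lower incidence of adverse effects".
- **Theoretical framework and empirical evidence** mentions another possible route, as background: "weekly doses optimize absorption through transport mechanisms, decreasing intolerance symptoms".
- **Operational definition of variables** grades adherence. The low class begins "We will consider low adherence the consumption of less than 50% of the amount of medication" and also requires under half of the intakes; the high class requires more than 80% of both; and "All combinations not covered by low and high adherence will be considered as moderate adherence". These classes are not tied to a per-protocol set.
- The **elimination criteria** and **Record of adverse effects** remove infants with intolerance to iron from the study. The first says severe intolerance; the second says intolerance without that qualifier.
- In EBF the reference category is no supplementation; in MF it is daily iron.

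**The concern.** In many trials non-adherence is a nuisance that dilutes the effect, and a per-protocol result close to ITT is reassuring. Here, by the trial's own hypothesis, differential adherence and tolerability are how weekly iron is meant to win. Restricting both arms to infants who took their iron equalises what is supposed to differ. If the hypothesis is right, ITT should favour weekly iron and per-protocol should show less. Read by the stated criterion, that pattern would count against robustness although it is the predicted one. If the two schedules were equally effective and equally well taken, both analyses would show no difference and would agree, which says nothing about robustness either.

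There is a separate issue in EBF. A set built on intake would select families in the two iron arms but could not select, by intake, in the untreated reference arm. The contrast would then set adherent families against an unselected control.

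At stake is the reading of the trial's general objective, the effectiveness of weekly against daily iron. ITT addresses the effect of assigning a schedule; per-protocol addresses the effect when the schedule is followed. These are different questions.

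**Working it through.** **The plan's own figure.** Inputs from Sample size and selection: 50.8% and 30%, power 0.80, and the stated 0.95 read as 95% confidence (two-sided alpha 0.05). With mean proportion 0.404:

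n = [1.96·√(2·0.404·0.596) + 0.8416·√(0.508·0.492 + 0.30·0.70)]² / 0.208² = 86.2, so 87 per group and 174 in total, as stated. 174/0.85 = 204.7, against 204 stated, which is immaterial. The calculation is used here only for its two event rates.

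**Weekly against daily, benefit through adherence only.** Assumptions: 30% is the risk in infants who take iron and 50.8% in those who do not; both schedules work equally well when taken; adherence a is illustrative, since the protocol gives no rates.

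ITT arm risk = a·0.30 + (1 − a)·0.508; per-protocol arm risk = 0.30.

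| Adherence weekly / daily | ITT risks | ITT RR | Per-protocol RR |
|---|---|---|---|
| 80% / 50% | 34.2% vs 40.4% | 0.85 | 1.00 |
| 90% / 60% | 32.1% vs 38.3% | 0.84 | 1.00 |
| 70% / 60% | 36.2% vs 38.3% | 0.95 | 1.00 |
| 90% / 50% | 32.1% vs 40.4% | 0.79 | 1.00 |
| 90% / 30% | 32.1% vs 44.6% | 0.72 | 1.00 |

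In the first row, per-protocol drops 20% of weekly and 50% of daily infants.

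**With an additional absorption benefit.** Let the risk when weekly iron is taken be lower than 30% (assumed), with daily kept at 30%.

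| Weekly risk if taken | Adherence weekly / daily | ITT RR | Per-protocol RR |
|---|---|---|---|
| 25% | 90% / 50% | 0.68 | 0.83 |
| 20% | 90% / 50% | 0.57 | 0.67 |
| 20% | 80% / 60% | 0.68 | 0.67 |

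In the first two rows the effect is attenuated, not removed. In the last the analyses nearly coincide although adherence differs by 20 percentage points: the two pathways happen to balance.

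**EBF, iron against none.** With 70% adherence, the ITT risk is 0.7·0.30 + 0.3·0.508 = 36.2%, RR 36.2/50.8 = 0.71; the per-protocol RR is 30/50.8 = 0.59. Here per-protocol moves away from the null. Selection alone can do the same: if iron had no effect, but families who adhere had an underlying risk of 45% (assumed) against 50.8% overall, the ITT RR would be 1.00 and the per-protocol RR 45/50.8 = 0.89.

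**Precision.** At 87 per group, the 80%/50% case gives SE(log RR) = √[0.658/(87·0.342) + 0.596/(87·0.404)] = 0.198, so RR 0.85 has a 95% CI of about 0.57 to 1.25. By normal approximation, counting both tails, power is about 14% in the first two rows of the first table and 6% in the third.

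**The case against.** The strongest reply is that the protocol never defines the per-protocol set. The only departures named alongside ITT are changes of feeding type or arm, and the adherence classes are not linked to any analysis set. A set that dropped only those changes would not select on missed intakes, and the point would weaken. This stands as a condition. The usual meaning of per-protocol does include taking treatment as assigned, and the robustness purpose is stated in the protocol itself, whatever a later document may define.

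A reader might infer that per-protocol erases the effect under test. The protocol does not support that in general. It holds only if the entire benefit runs through adherence and tolerability, and the background section offers absorption as another route.

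A reader might also infer a rule under which a correct ITT result would be discounted, or an EBF per-protocol result preferred. There is none: ITT is the stated analysis, no consequence is attached to disagreement, and adherence and adverse effects are themselves compared between schedules, which would help explain a divergence.

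The illustration is also favourable to the concern. The 30% is a group-level planning figure, not a risk in infants who took iron. If infants who under-take iron kept half the benefit (risk 40.4%, assumed), the 80%/50% ITT RR would be 32.1/35.2 = 0.91. Reminders and weekly contact may narrow the adherence gap. With power of about 6% to 14% in the first three scenarios, a clear ITT benefit beside a null per-protocol result would seldom be seen. All of this limits the size of the problem, not its logic.

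Finally, in EBF, changes of feeding or arm could remove controls too, so the selection is one-sided only as regards intake.

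**Conclusion.** The point holds in a limited form. With per-protocol in its usual sense, comparing it with ITT is not a valid robustness check for weekly against daily iron, because the hypothesis itself predicts divergence. Under the stated assumptions the ITT RR is 0.72 to 0.95 where the per-protocol RR is 1.00. With an absorption benefit the gap shrinks and can nearly close. The EBF contrast with no iron is a different matter: attenuation does not apply there, but selection by intake falls on the iron arms only.

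These figures rest on assumed adherence rates, on 30% and 50.8% as risks with and without iron, and on an intake-based set. They show direction, not a forecast. The consequence is for interpretation, since ITT remains the main analysis.

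One further limit affects the remedy. Because infants with intolerance leave the study, ITT may itself lose part of the tolerability pathway, so pointing to ITT is not enough unless those infants are kept in it.

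**What to change.** 1. In Data analysis, delete the closing clause that makes the comparison with per-protocol a test of robustness.
2. State that the weekly-daily conclusion, and iron versus none in EBF, rest on ITT.
3. Label per-protocol as a supplementary estimate of the effect when iron is taken as assigned, and report the number removed in each arm.
4. State that infants who stop for intolerance are analysed in their randomized group wherever a 6-month outcome is available, and reconcile this with the exclusion wording in the elimination criteria and Record of adverse effects. This concerns the analysis only, not how those infants are treated.
5. Judge robustness by sensitivity analyses for missing outcomes that keep all randomized infants.

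Adjusting the per-protocol estimate for 3-month hemoglobin, ferritin and maternal education, which are already collected, is optional. It may reduce selection bias but cannot restore an effect that passes through adherence.

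The cost is a few sentences and the sensitivity analyses. No extra infants are needed, though 6-month results for infants who stop must be kept where they exist. The sponsor gives up the simple statement that both analyses agree.
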